### 15.7. Pharmacodynamic Analysis

PD analyses will be based on the FAS. Select secondary and exploratory PD endpoint analyses may also be repeated in the PP Set, if sufficiently different to the FAS, as supportive analyses.

PD analyses will compare placebo and EP262 descriptively. No formal statistical testing will be performed. For select PD endpoints, the 90% confidence interval and/or nominal p-values will be presented.

For select endpoints, absolute, percent change, and/or fold-change from baseline will be summarized. Correlation analysis between responses in disease severity scores and changes in select PD parameters may be explored. Additional information will be provided in the SAP.

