# 15.10. Multiple Comparison/Multiplicity

No adjustment for multiplicity will be performed due to the hypothesis generating nature of this study.

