1. INTRODUCTION

The purpose of this Statistical Analysis Plan (SAP) is to provide comprehensive and detailed descriptions of the methods and presentation of data analyses proposed for Escient Pharmaceuticals, Inc. Protocol EP-262-202 (Phase 2a, Randomized, Double-Blind, Placebo-Controlled Study to Evaluate the Safety, Tolerability, and Pharmacodynamics of EP262 in Subjects with Atopic Dermatitis). Descriptions of planned analyses are provided in order to avoid post hoc decisions that may affect the interpretation of the statistical analysis. The statistical methods applied in the design and planned analyses of this study are consistent with the International Council for Harmonisation (ICH) guideline *Statistical Principles for Clinical Trials (E9)* (1998) and *Statistical Principles for Clinical Trials: Addendum: Estimands and Sensitivity Analysis in Clinical Trials (E9[R1], Rev 1)* (2021).

This SAP will be finalized prior to data analysis and before treatment unblinding and database lock to provide comprehensive details of the tables and listings to be presented in the Clinical Study Report (CSR). Any changes between the statistical methods provided in the clinical study protocol and this SAP will be explained herein; any changes or deviations from this SAP relative to the final analysis will be fully documented in the CSR. Minor changes or deviations from the templates for tables and listings need not be documented in the CSR.

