No formal statistical analysis will be performed to compare treatment groups. This study is exploratory in nature; descriptive statistics will be tabulated by treatment group and reviewed to evaluate all study endpoints. Any p-values presented are to be considered nominal in their evaluation and interpretation. P-values will be reported for statistical tests, rounded to four decimal places. P-values less than 0.0001 will be displayed as “<0.0001”; p-values greater than 0.9999 will be displayed as “>0.9999”.

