4.4.3 Pharmacodynamic Analysis Methods

4.4.4 *Statistical/Analytical Issues*

4.4.4.1 *Adjustments for Covariates*

The ANCOVA model to compare treatment groups for the skin biopsy-derived biomarkers secondary endpoint of skin histology will include a covariate adjustment for the baseline value. All statistical results presented are to be considered nominal in their evaluation and interpretation.

4.4.4.2 *Handling of Dropouts or Missing Data*

No imputations will be performed on missing data; all analyses will be descriptive in nature and based on observed data only. Any responder analysis will be based on the number of subjects reporting data at the visit of interest.

4.4.4.3 *Interim Analyses and Data Monitoring*

No interim analysis will take place for the study.

4.4.4.4 *Multicenter Studies*

This is a multicenter study to be conducted within North America. Pharmacodynamic data collected from all study sites will be pooled for data analysis. The effect of study site on the analysis results may be explored post-hoc, as needed.

4.4.4.5 *Multiple Comparisons/Multiplicity*

[figure not shown]
For analysis of gene expression, the Bonferroni correction will be used to control the alpha at 5%. For analysis of other parameters, there will be no adjustments for multiple comparisons in the analysis for this study. Results are descriptive in nature and there will be no formal comparisons made among treatment groups. All statistical results presented are to be considered nominal in their evaluation and interpretation.

4.4.4.6 *Use of an “Efficacy Subset” of Subjects*

The primary analysis will be performed on the FAS; the PP Set will be utilized as a sensitivity analysis. The PP Set will exclude subjects with IPDs.

4.4.4.7 *Active-Control Studies Intended to Show Equivalence*

This study does not include an active-control product and is not intended to demonstrate equivalence between any two drug products.

Additional subgroup analyses may be performed post-hoc, as appropriate.

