4.7 Changes in the Conduct of the Study or Planned Analyses

Section 15.11 of the clinical study protocol defines the following planned interim analysis:

Given the hypothesis-generating nature of this study, an interim analysis may be conducted. The interim analysis would evaluate the effects of EP262 on select PD endpoints and safety.

The decision to conduct an optional interim analysis and the timing of the analysis will be documented in the study files prior to conduct of the interim analysis. The SAP will be amended if emerging data from the completed interim analysis leads to substantial change in the study protocol that has significant impact on the statistical analyses.

No interim analysis will be conducted for the study.

Section 15.7 of the clinical study protocol defines the following planned PD analysis:

PD analyses will compare placebo and EP262 descriptively. No formal statistical testing will be performed. For select PD endpoints, the 90% confidence interval and/or nominal p-values will be presented.

When confidence intervals are presented for PD endpoints, the SAP includes a 95% confidence interval across all parameters.

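### SAP 4.4.4.5 applies Bonferroni to gene expression although protocol 15.10 rules out adjustment, SAP 4.7 does not list the change, and for a many-gene screen false discovery rate control would suit better

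*SAP*

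**What the plan says.** Protocol 15.10 makes no exception for any endpoint: "No adjustment for multiplicity will be performed due to the hypothesis generating nature of this study". Protocol 15.7 plans descriptive PD comparisons without formal testing and adds: "For select PD endpoints, the 90% confidence interval and/or nominal p-values will be presented".

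SAP 4.4.4.5 treats gene expression differently from everything else: "For analysis of gene expression, the Bonferroni correction will be used to control the alpha at 5" per cent. Other parameters get no adjustment. The same paragraph continues: "Results are descriptive in nature and there will be no formal comparisons made among treatment groups". SAP 4.1.1 says of the whole analysis: "Any p-values presented are to be considered nominal in their evaluation and interpretation".

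On departures from the protocol, SAP 1 promises: "Any changes between the statistical methods provided in the clinical study protocol and this SAP will be explained herein". SAP 4.7 is the section for them. It records that no interim analysis will be done, and it records the move from 90% to 95% intervals: "When confidence intervals are presented for PD endpoints, the SAP includes a 95% confidence interval across all parameters". It does not mention Bonferroni.

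The body of SAP 4.4.3, which the contents list places on pages 24 to 28, is not shown in this copy. The visible text gives neither the number of genes nor the gene-level test.

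**The concern.** There are two separate matters.

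The first is documentary. The SAP reverses a protocol rule for part of the secondary endpoint, and the section that records such reversals omits it. A change of confidence level was thought worth listing, so a change of error-control policy belongs there too.

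The second is the choice of method. The protocol synopsis (Skin Punch Biopsies) names transcriptomics, and the SAP abbreviation list includes differentially expressed, rlog and vst. A family of thousands of genes is therefore possible, though not certain. Bonferroni guards against a single false positive anywhere in the family. A hypothesis-generating screen usually wants a list that holds most of the changed genes, with a known and tolerable share of false ones. With about 30 subjects randomised 2:1, a family-wise cut-off over thousands of genes could leave most of the changed genes off the list.

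**Working it through.** The documents give no gene count, effect size or power figure, so there is no plan figure to reproduce. What follows is conditional.

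**Inputs from the documents.** About 30 subjects randomised 2:1, so 20 v 10 if all are evaluable; Bonferroni at 5%.

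**Assumptions.** Two-sided two-sample t-test on change from baseline (28 df); independent genes; m = 5,000 to 15,000 genes; 5% truly changed, all by d standard deviations.

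**Bonferroni.** The per-gene level is 0.05/m.
- m = 5,000: 0.05/5,000 = 0.00001, critical t = 5.37.
- m = 15,000: 0.05/15,000 = 0.0000033, critical t = 5.78.
- Noncentrality is d/√(1/20 + 1/10): 1.5/0.387 = 3.87 at 1.5 SD and 2/0.387 = 5.16 at 2 SD.

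Both values lie below the critical t, so per-gene power is under one half.

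**Benjamini-Hochberg at 5%.** With many genes the p-value cut-off t settles where t / (0.95t + 0.05 × power(t)) = 0.05.
- 1.5 SD: t = 0.0017, power 65.5%. Check: 0.00172/(0.00163 + 0.0327) = 0.050.
- 2 SD: t = 0.0025, power 95.6%. Check: 0.00251/(0.00238 + 0.0478) = 0.050.

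Share of truly changed genes found, 20 v 10, 5% changed:

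| Effect | Bonferroni, 5,000 genes | Bonferroni, 15,000 genes | Benjamini-Hochberg |
|---|---|---|---|
| 1.0 SD | 1.2% | 0.6% | 7–8% |
| 1.5 SD | 11.8% | 7.0% | about 66% |
| 2.0 SD | 44.9% | 32.9% | about 96% |
| 3.0 SD | 97% | 94% | about 100% |

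Simulation with independent genes agreed with these figures to about a point.

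**In genes.** With 15,000 genes, 750 are changed. At 1.5 SD Bonferroni finds 750 × 0.070 ≈ 53. Benjamini-Hochberg finds 750 × 0.655 ≈ 491, plus 14,250 × 0.00172 ≈ 25 false ones (25/516 ≈ 5%).

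**Sensitivity to the assumptions.**
- More genes: at 1.5 SD Bonferroni falls to 6% with 20,000 genes and 5% with 30,000.
- Fewer changed genes (1% of 15,000, 1.5 SD): 7% v 38%.
- Fewer evaluable subjects (16 v 8, 15,000 genes): about 3% v 42% at 1.5 SD and 14% v 86% at 2 SD. This matters because of SAP 4.4.4.2: "No imputations will be performed on missing data; all analyses will be descriptive in nature and based on observed data only".
- Short panel (50 genes, 10% changed): 58% v 77% at 1.5 SD, 91% v 98% at 2 SD.
- Paired contrast, effect in SD of the paired difference, noncentrality d√n. With 20 pairs Bonferroni finds 73% (5,000 genes) or 59% (15,000) at 1.5 SD, and 99% or 96% at 2 SD. With 30 pairs it finds 99% or 98% at 1.5 SD.

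**Direction.** Benjamini-Hochberg's strictest step is 0.05/m, which is the Bonferroni cut-off. Any gene that Bonferroni flags, Benjamini-Hochberg at 5% also flags.

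**The case against.** The case for leaving the plan alone has real force.

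- A reader might infer that the SAP gives no reason for Bonferroni. The documents do not support that. SAP 1 promises an explanation somewhere in the SAP, not only in 4.7, and the methods text of 4.4.3 is not shown. Only the omission from 4.7 can be established.
- A reader might infer that the plan will miss most changed genes. That does not follow either. The endpoint is called a signature, which could be a short prespecified set. Protocol 5.2 speaks of lesional relative to nonlesional skin before and after treatment, so paired contrasts are as plausible as a between-arm one, and they do much better at the same number of SDs. A model that shares variance across genes would raise power for both methods.
- A reader might call 4.4.4.5 self-contradictory because it controls alpha and also calls the results nominal. The fit is awkward, but limiting a gene list while treating it as descriptive is not a contradiction.
- Bonferroni is valid and errs on the strict side, no visible decision rule depends on the list, and Benjamini-Hochberg would itself depart from protocol 15.10.

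All of this stands, and it limits the size of the point. It does not remove the conflict with 15.10 or the gap in 4.7. Nor does it show Bonferroni to be the better tool if the family is large.

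**Conclusion.** The conflict between SAP 4.4.4.5 and protocol 15.10, and its absence from SAP 4.7, hold on the visible text without assumptions. The cost of the method is conditional. For a between-arm comparison of 20 v 10 over 5,000 to 15,000 independent genes with 5% changed, Bonferroni would list about 7–12% of the changed genes at 1.5 SD and 33–45% at 2 SD, where Benjamini-Hochberg would list about 66% and 96%. At 1 SD the sample size limits both methods. With effects near 3 SD little is lost, and a short panel or a paired contrast loses less at the same 1.5 to 2 SD. Gene count, effect size, share changed, contrast and complete biopsies are all assumed. The point is a cheap improvement of minor to moderate weight. It does not show that the planned analysis is invalid.

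**What to change.** If many genes are tested, replace the Bonferroni sentence in SAP 4.4.4.5 with wording such as: gene-level p-values will be adjusted across the genes tested by the Benjamini-Hochberg procedure at a 5% false discovery rate, and shown beside the raw nominal p-values and log2 fold changes. State there, or by cross-reference to 4.4.3, the set of genes and the contrast that form the family. List the change in SAP 4.7 as a departure from protocol 15.10, since Benjamini-Hochberg is also an adjustment.

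If Bonferroni is kept, for example for a small prespecified signature, list it in SAP 4.7 with the reason and show the raw nominal p-values beside the adjusted ones.

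The cost is SAP wording and one line of code, to be settled before unblinding. The statistical price is that on average up to about 5% of flagged genes are false positives, and the share varies more when genes are co-expressed. In simulations with within-block correlation 0.5 (5% changed, 1.5 to 2 SD) the mean stayed at 4.3–5.2%. The 5th to 95th percentile ran from about 3–7% (15,000 genes, blocks of 50) to 0–16% (5,000 genes, blocks of 500).

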4.4.5 Plasma Concentrations

Raw plasma concentration values will be summarized for the PK Set by treatment group and sampling time point using descriptive statistics, to include the geometric mean and CV (%). For summaries of plasma concentrations, below the limit of quantification (BLQ) values will be set to missing. The number and percentage of subjects with BLQ values will be summarized by time point and treatment group.

4.4.6 Pharmacokinetic Analysis

Pharmacokinetic analysis is based on the analysis of plasma concentrations of EP262 as described in [Section 4.4.5](#).

4.5 Safety Evaluation

Safety analysis will be carried out for the Safety Analysis Set, to include all subjects who receive at least one dose of study drug. Subjects who do not complete the study, for whatever reason, will have all available data up until the time of termination included in the analysis, as described in [Section 4.1.2](#). For safety analysis presented by study visit, the baseline value will be defined as the last value reported prior to first dose of study drug.

4.5.1 Extent of Exposure

Extent of exposure to study treatment will be summarized for the Safety Analysis Set by treatment group and overall subjects combined. The duration of exposure will be presented in days and calculated as the date of last dose of study drug minus the date of first dose of study drug, plus one. Total dose received (mg) will be determined as the summation of all entries of “Dispensed Amount (Capsules)” reported on the “Drug Accountability – Dispensed” eCRF minus the summation of all entries of “Amount Returned (Capsules)” reported on the “Drug Accountability – Returned” eCRF. Any capsules reported as lost will be further subtracted from this total. Subjects that are missing their return records are assumed to have taken all dispensed capsules for the missing bottle. The number of capsules taken is then multiplied by 75 to obtain the total dose received (mg). Duration of exposure and total dose received (mg) will be summarized using descriptive statistics.

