# 10.6. Study Drug Handling and Disposal

Study drug will be sent to the clinical site under appropriate storage conditions. Upon receipt of study drug, site staff are to open the shipment, and verify that the amount and identity of the contents match that stated in the enclosed shipping form. The Sponsor (or designee) is to be notified immediately about any irregularities, discrepancies, or damage.

Study drug will be provided for use only in this study and is not to be used for any other purpose. The site staff will maintain a full record of study drug accountability as described in Section 10.5.

Upon completion of the study, used and unused study drug and study drug bottles are to be returned to the Sponsor (or designee) or, if prior Sponsor approval is obtained, disposed of in accordance with applicable site procedures. Site staff must maintain documentation of any missing or unreturned study drug. The final disposition of all study drug received at the site is to be documented.

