# **Summary of Changes for Amendment 1.0 Dated 02 August 2023**

Protocol EP-262-202 was amended to address the following changes, including:

- Criteria for study drug discontinuation were updated
- Photographs will not be taken until a subject is enrolled in the study, the protocol was updated accordingly
- Urine albumin was removed from the urinalysis panel

Notable changes are included below in the summary table. Revised text in Amendment 1.0 is bolded, and text deleted from the original version is crossed out in the table below. Italicized text is used to describe a change. Minor/editorial changes are not listed individually in the summary table.

Section	Original	Amendment 1.0	Reason for Change
Title page Sponsor Statement	New text	Study Acronym: EASE	The study acronym was added to further denote the study title.
Synopsis, Study Drug Section 10.1, Study Drug	Study Drug Capsules containing 75 mg of EP262 or placebo will be supplied in bottles in a manner to ensure the study blind. Each subject will take 2 capsules per dose for a total of 150 mg per day.	Study Drug Capsules containing 75 mg of EP262 or placebo will be supplied in bottles in a manner to ensure the study blind. Each subject will take 2 capsules per dose, with subjects randomized to EP262 receiving a total of 150 mg per day.	Text was added to clarify that only subjects randomized to the EP262 group will receive active drug.

Evaluations of Safety  esterase, nitrites, pH, protein, specific gravity, glucose, occult blood, ketones, bilirubin, urobilinogen, and albumin; microscopic analysis is to be performed  esterase, nitrites, pH, protein, specific gravity, glucose, occult blood, ketones, bilirubin, and urobilinogen; microscopic analysis is to be performed only if protein,	Section	Original	Amendment 1.0	Reason for Change

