3.3 Treatment

3.3.1 Treatment Administered

Capsules containing 75 mg of EP262 or placebo will be supplied in bottles in a manner to ensure the study blind. Each subject will take 2 capsules per dose, with subjects randomized to EP262 receiving a total of 150 mg per day.

Each study drug dose is to be administered PO as intact capsules (swallowed whole, not split, opened, or chewed) and taken with approximately 240 mL (8 fluid ounces) of water on an empty stomach. Subjects will be instructed to take the study drug at approximately the same time of the day after a fast of at least 4 hours. Subjects should refrain from eating for at least 2 hours postdose. On the days of clinic visits, the time of study drug administration may differ depending on the scheduled visit time. The first

dose of study drug will be administered at the clinical site on Visit 2 (Day 1) after all baseline study procedures are completed.

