4.2 Analysis Sets

The analysis sets are defined as follows:

- **Full Analysis Set:** All subjects who are randomized and take at least 1 dose of randomized study drug will be included in the Full Analysis Set (FAS). Subjects in the FAS will be analyzed according to randomized treatment assignment. All PD analyses will be based on the FAS.
- **Per Protocol Set:** The Per Protocol (PP) Set is a subset of the FAS containing subjects who meet study eligibility requirements and had no protocol deviations that might impact the assessment of PD measurements. Subjects will be analyzed according to randomized treatment assignment. The PP Set will be used for sensitivity analyses relating to PD. Protocol deviations that qualify for exclusion from the PP Set include:
 - Deviations of inclusion/exclusion criteria
 - Non-permitted concomitant medications or procedures that may meaningfully impact PD outcomes
 - Meaningful dosing and/or randomization error(s)
 - Any other important protocol deviation deemed by the Sponsor to warrant exclusion from the PP set

Any protocol deviations that govern exclusion from the PP Set will be determined prior to database lock.

- **Safety Analysis Set:** All subjects who are randomized and take at least 1 dose of randomized study drug will be included in the Safety Analysis Set. Safety analyses will be based upon treatment actually received.
- **PK Set:** All subjects who receive at least 1 dose of EP262 and provide adequate blood samples for bioanalysis will be included in the PK Set.

Data summaries to be presented on both the Safety Analysis Set and the FAS will only be produced on both analysis sets if there is a difference in the population groups.

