4.5.2 Measurements of Treatment Compliance

4.5.2.1 Study Treatment Compliance

Compliance to the study treatment regimen will be based on the drug accountability records. Compliance will be determined as the percentage of expected capsules that a subject should have taken based on their dosing days on study relative to the drug accountability reporting of their actual number of capsules taken. The following definitions are applied:

- **Expected Number of Dosing Days:** the last dose date reported on the End of Treatment eCRF minus the onsite first study administration that takes place at Visit 2 (Day 1) + 1.
- **Expected Number of Capsules to be Taken:** Expected Number of Dosing Days multiplied by two (standard dosing includes two capsules per day).
- **Actual Number of Capsules Taken:** The summation of all entries of “Dispensed Amount (Capsules)” reported on the “Drug Accountability – Dispensed” eCRF minus the summation of all entries of “Amount Returned (Capsules)” reported on the “Drug Accountability – Returned” eCRF. Any capsules reported as lost will be further subtracted from this total. Subjects that are missing their return records are assumed to have taken all dispensed capsules for the missing bottle.

Treatment compliance (%) is defined as the Actual Number of Capsules Taken divided by the Expected Number of Capsules to be Taken, multiplied by 100.

Dosing compliance will be summarized using descriptive statistics, by treatment group and overall subjects combined, for the Safety Analysis Set. The number and percentage of subjects who are < 80% compliant and ≥ 80% compliant within each treatment group and overall subjects combined will be summarized.

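### SAP 4.5.1 converts every subject's capsules to mg at 75 mg each, so the total-dose row, as written, gives placebo subjects a mg dose they did not receive

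*SAP*

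**What the plan says.** SAP 4.5.1 sets the population and columns of the exposure table: "Extent of exposure to study treatment will be summarized for the Safety Analysis Set by treatment group and overall subjects combined". Under SAP 4.2 the Safety Analysis Set is every randomized subject with at least one dose, so it includes the placebo arm.

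Capsules taken are capsules dispensed, minus capsules returned, minus capsules reported lost. The conversion follows: "The number of capsules taken is then multiplied by 75 to obtain the total dose received (mg". The section closes with: "Duration of exposure and total dose received (mg) will be summarized using descriptive statistics". No sentence restricts the factor by treatment, marks placebo as not applicable, or says that the mg figure is nominal.

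SAP 3.3.1, in the same words as Protocol 10.1, has all subjects take two capsules per dose but attaches the mg dose to one arm: "with subjects randomized to EP262 receiving a total of 150 mg per day". The reason recorded for that wording in the protocol's summary of changes for Amendment 1.0 is: "Text was added to clarify that only subjects randomized to the EP262 group will receive active drug". The log is cited here only for the sponsor's stated intent; the current text makes the point without it.

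SAP 4.2 adds for safety outputs: "Safety analyses will be based upon treatment actually received". SAP 4.1.1 gives every table outside the pharmacodynamic and pharmacokinetic analyses a column for all subjects combined.

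**The concern.** The conversion factor is the EP262 content of an active capsule. Applied to placebo capsules, it yields a quantity that the treatment description does not recognise. A programmer who follows SAP 4.5.1 exactly would fill the placebo column with values close to those of the EP262 column. The pooled column would then average real and notional milligrams.

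What is at stake is how one row of a safety table reads. Safety and tolerability is the primary objective, and the exposure table is its basic context. A row labelled as dose received in mg should not credit drug to subjects who received none.

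**Working it through.** **Inputs**

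- 75 mg per EP262 capsule and 2 capsules per dose: SAP 3.3.1, Protocol 10.1.
- Once-daily dosing for 6 weeks, so 42 days: SAP 3.3.2.
- About 30 subjects randomized 2:1, so 20 EP262 and 10 placebo: SAP 3.3.2.
- Visit 4 at Day 43 ± 3 days: Protocol Appendix A.
- Assumptions: full adherence, all subjects in the Safety Analysis Set, equal exposure in the two arms.

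**Step 1. Reproduce the plan's own figure.** 2 capsules × 75 mg = 150 mg per day. This matches the daily dose stated for EP262 subjects.

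**Step 2. Apply the rule as written.** Total = days × 2 × 75. For 42 days this is 84 capsules × 75 = 6,300 mg. Nothing in the rule depends on treatment, so the EP262, placebo and overall means are all 6,300 mg.

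**Step 3. Count only EP262.** EP262 arm: 6,300 mg, unchanged. Placebo arm: 84 × 0 = 0 mg. Overall mean: (20 × 6,300 + 10 × 0) / 30 = 4,200 mg.

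**Step 4. Compare.** 6,300 / 4,200 = 1.5. In general, with arm sizes n and mean capsules c, the ratio of the overall mean as written to the EP262 actually taken per subject is 1 + (n_placebo × c_placebo) / (n_EP262 × c_EP262). With equal exposure this is 1 + 10/20 = 1.5, whatever the duration. It moves if exposure differs between arms. For example, if placebo subjects took 80% as many capsules as EP262 subjects (an assumed figure), it is 1 + 0.5 × 0.8 = 1.4.

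**Step 5. Vary the duration.** Visit 4 may fall on Days 40 to 46. A last dose on the day before gives 39 to 45 dosing days; a dose on the latest permitted day gives 46.

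| Dosing days | Placebo, as written (mg) | EP262 in placebo arm (mg) | Overall mean, as written (mg) | Overall mean, EP262 only (mg) |
|---|---|---|---|---|
| 39 | 5,850 | 0 | 5,850 | 3,900 |
| 42 | 6,300 | 0 | 6,300 | 4,200 |
| 45 | 6,750 | 0 | 6,750 | 4,500 |
| 46 | 6,900 | 0 | 6,900 | 4,600 |

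**Step 6. Look for other uses of the mg figure.** Duration of exposure in SAP 4.5.1 is a difference of dates. Compliance in SAP 4.5.2.1 is a ratio of capsule counts. No adverse event, laboratory or pharmacodynamic output visible in the SAP uses total mg.

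**The case against.** The best defence is that the row is meant as a nominal study-drug dose. Study drug covers EP262 and placebo throughout the protocol, the section speaks of exposure to study treatment, and both arms take matching capsules. On that reading the mg total is a capsule count on another scale, and no figure is false. The reading is possible, but the SAP does not state it, and SAP 3.3.1 reserves the mg dose for the EP262 arm. If a nominal dose is intended, the row needs that label, so a clarifying sentence is needed either way.

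A second defence is that SAP Section 1 refers to templates for tables and listings, which are not in the documents. A footnote or a not-applicable entry there cannot be ruled out. That stands: the point concerns the written rule, not a table anyone has seen.

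A third is that the factor of 1.5 describes a pooled mg mean that has little use even when computed correctly, because it mixes zeros with full doses. That also stands, and it is why the remedy drops the pooled mg figure instead of correcting it.

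A reader might infer that the overall column conceals that one third of subjects were on placebo. It does not, because the same table has separate treatment-group columns.

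**Conclusion.** The rule in SAP 4.5.1, followed exactly, gives a figure that conflicts with the SAP's own account of who receives active drug. Under full adherence for 42 days and a 20:10 split, placebo subjects show 6,300 mg instead of none. The overall mean is 6,300 mg against 4,200 mg of EP262 received. The factor of 1.5 rests on equal exposure in the arms; the placebo discrepancy does not.

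The reach is one descriptive row. A reader might infer that the exposure or safety results as a whole are unreliable. The documents do not support this: the conversion leaves the EP262 column correct, and duration, compliance and the visible safety and pharmacodynamic outputs do not use the mg total. Nor is the handling of missing return records part of this error. That is a separate convention, stated in advance in both SAP 4.5.1 and 4.5.2.1. The point is of the lowest severity, but the written rule should still be corrected.

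**What to change.** Add to SAP 4.5.1 that the factor of 75 mg applies only to EP262 capsules, with subjects classified by treatment actually received, as SAP 4.2 already requires for safety outputs. Present total dose in mg for the EP262 group only, with placebo shown as not applicable and no overall mg figure. State this as an exception to the all-subjects column in SAP 4.1.1. Present the number of capsules taken for both groups and overall.

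The cost is a short addition to the SAP text and one programming condition. No new data are needed and nothing is lost, because capsule counts still show exposure in both arms. No protocol commitment is affected: Protocol 15.5 calls for compliance and duration of treatment and does not mention a total dose in mg.
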